#### 6 Materials

## 6.1 Device Description

The modified Venus Versa (MP) by Venus Concept Ltd. is a non-invasive dermatological treatment system based on patented and proprietary (MP) technology combines Multi Polar Radiofrequency (RF) and Pulsed Magnetic Fields. The RF energy penetrates the skin and resulted in RF-generated tissue heating that has known effect on skin laxity, the magnetic field that is simultaneously induced increases fibroblast collagen production through non-thermal mechanism and contributes to the clinical effect of skin laxity improvement. The system is paired with the Freeze Diamondpolar applicator (with 4 electrodes) which will be used to treat the mons pubis, vaginal introitus and labia. For the internal vaginal treatments, an investigational handpiece (applicator) will be used, however no change in range of energy modality or amount of energy delivered will occur at any point during the study.

#### 6.2 Measurement Equipment

### 6.2.1 Standard High Resolution Digital Camera

The investigative site will ensure the digital photography equipment including photo storage media and adequate lighting equipment is available for use during this study. Photographs of the treated areas will be taken at various visits as detailed in the schedule of events chart.

For consistency purposes, all images throughout the study must be taken, using the same camera and lighting settings, preferably by the same photographer, the photography should be taken from the same angle. Subject anonymity will also be assured for the images by deleting any ID detail. Only the code for the Case Number in the study will appear on the records being transferred to the sponsor.

Confidential 9

<sup>1 Noninvasive Radio Frequency for Skin Tightening and Body Contouring. Weiss, 2013

#### 6.2.2 pH Paper

The investigative site will ensure pH paper is available for use during this study. pH measurements will be taken at various visits as detailed in the schedule of events chart. For consistency purposes, all pH measurements throughout the study shall be taken from the mid posterior wall of the vaginal mucosa.

## 6.2.3 Histopathology and Molecular Studies

The investigative site will ensure Tischler biopsy forceps or the equivalent of a small punch biospsy (2-3mm) for skin/mucosal biopsy is available for use during this study. Histopathology and molecular study specimens will be taken at various visits as detailed in the schedule of events chart (Appendix A). For consistency purposes, all histopathology and molecular study specimens taken throughout the study shall be taken from any of the anatomic sites treated.

Subject anonymity will also be assured for histopathology slides and molecular assay results by deleting any associated ID detail. Only the code for the Case Number in the study will appear on the records being transferred to the sponsor.

## 7 Study Procedures

### 7.1 Study duration and timelines

Each subject will be enrolled and scheduled for three treatments at approximately four week intervals and return for a follow-up visit at one month (± seven days) after the last treatment for evaluation of the treated areas. During each visit various tasks will be performed as detailed in the study flow chart (Appendix A).

Each subject will therefore participate in the study for a period of at least 3 months. The study is anticipated to be completed within six months.

#### 7.2 Evaluation Assessments

Various assessments will be performed throughout this clinical study. The grading of the photographs of the treated area will be performed by independent evaluators. See Table 1.

#### 7.2.1 Post Treatment Responses

Immediate and short term responses (erythema, edema, purpura, etc.) will be assessed by the investigator immediately and up to 30 min post treatment, by a 5 level scale: 1=none; 2=trace; 3=moderate; 4=marked; 5=severe.

In addition, subject reporting on duration of post-treatment adverse events questionnaire will be collected after each treatment and at the follow-up visit.

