### 2 Study Design

This is a single center, baseline-controlled, prospective study. Ten (10) and up to three hundred (300) subjects that meet the inclusion criteria will be enrolled from the site's pool of patients. Subjects should be female, at the age of 25-65 years, and have a suitable treatment area (e.g. skin irregularities and/or unwanted skin laxity in the mons pubis, introitus and/or labia area).

Subjects will receive three treatments with the study device and both applicators, at four week intervals, followed by one month follow-up visits after the last treatment.

Confidential 6

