### 4.3 Safety Endpoint

- Immediate and short term response as assessed by the investigator following treatment, defined as type and intensity of response and the time it takes for it to subside.
- Any adverse events associated with various setting(s) used during the treatment and follow-upperiod.

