## 7.2.4.2 Level of improvement and satisfaction

Subject's Improvement and Satisfaction with treatment will be recorded by using the GAI scale at the last follow up visit (see Appendix B).

Table 1 - Clinical Evaluation Tools

Claim/task	When to conduct?	Tool		
Photography	Baseline, immediately before	Standardized digital photographs		
	treatments 2, 3, FU 3			
Vaginal pH	Baseline, immediately before	Standard pH paper		
	treatments 2, 3, FU 3			
Histopathology & Molecular	Baseline, immediately before	Histology slides, special staining		
Studies	treatments 2, 3, FU 3	and assays.		
Immediate and short term	Immediately following treatments	Examination of skin in the treated		
response evaluation by	1-3	area based on 5 level scale		
investigator		(Appendix F)		
Subject's duration of post-	Before treatments 2, 3, FU 3	Subject Questionnaire on post		
treatment adverse events questionnaire		treatment response (Appendix G)		
Subjects discomfort/pain	Immediately following treatments	VAS (Appendix E)		
assessment	1-3			
Subjects improvement/	FU3.	GAI (see Appendix B)		
satisfaction assessment				
score				
Independent reviewers score	At the end of the study	GAI (see Appendix B)		

Confidential 11

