#### 7.4 Pre-Treatment Procedures

#### 7.4.1 Subject Skin care and medication

- Before attending the first treatment, the subject will shave the treatment area at home, using foam or gel to minimize skin irritation.
- Apply medical Grade Glycerin on the treated area

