## 9.3 Risk/ Benefit Analysis

#### 9.3.1 Risks

The potential risks for adverse effects of the treatment procedure include but are not limited to mainly to transient edema or erythema in the treated area the following events were also identified as low probability anticipated adverse effects: pain, tenderness, erythema lasting longer than 6 hours, mild to moderate edema lasting more than 6 hours, burn, blistering, crusting, hyperpigmentation, hypopigmentation, scarring, potential damage to hair follicles and loss of hair within the treatment zones and eye irritation. (See Appendix I for Additional Safety Background).

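### The investigator's reaction score is taken only after treatment, so redness, swelling or bruising already present cannot be separated from device response in the recorded data

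*Combined protocol and SAP*

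**What the plan says.** Section 4.3 lists as a safety endpoint "Immediate and short term response as assessed by the investigator following treatment, defined as type and intensity of response", together with the time the response takes to subside. The synopsis places the same item among the secondary endpoints.

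The timing is the same wherever the score is scheduled:

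- Section 7.2.1: erythema, edema, purpura and similar reactions "will be assessed by the investigator immediately and up to 30 min post treatment, by a 5 level scale", with levels "1=none; 2=trace; 3=moderate; 4=marked; 5=severe".
- Table 1: "Immediately following treatments" 1 to 3.
- Section 7.5, step 8: the investigator examines the area once the external and the internal treatment are both finished.
- Appendix F: one circled number for the immediate response and one at about 30 minutes.
- Flow chart (Appendix A): one entry for this score at each of the three treatment visits, with no separate pre-treatment entry.

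The plan also provides for two things that can mark the tissue before a session. Under section 7.4.1, before the first treatment "the subject will shave the treatment area at home, using foam or gel to minimize skin irritation". Under section 6.2.3 and Table 1, specimens are taken by biopsy forceps or a small punch (2-3 mm) from treated sites, at baseline and immediately before treatments 2 and 3.

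Section 8.3 summarises the scores descriptively. It also uses the reactions and adverse events after treatment 1 for an interim safety report that guides adjustment of later treatment parameters.

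**The concern.** Safety is a primary objective and there is no control arm. A post-treatment score therefore has to be read against the state of the same tissue just before the session, and that state is not recorded on this scale. Shaving can leave redness, and a biopsy can leave redness, swelling or bruising. These are the signs that the score covers.

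The error could go either way. An investigator who does not allow for prior redness overstates the device reaction. One who puts a genuine reaction down to the razor or the biopsy understates it. The recorded number looks the same in both cases.

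The score also has a use during the study. The treatment 1 data inform later parameters, and treatment 1 is the session preceded by both shaving and the baseline specimen. Appendix I adds that the IRB will review safety results from the first 10 patients when an expansion to as many as 300 is submitted. If the scores are among those results, the ambiguity goes with them.

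**Working it through.** The plan states no figure for this score, so there is none to reproduce. The check is a count, a comparison of passages and one illustration.

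**1. Scores planned.** Inputs: 10 subjects (section 8.2), 3 treatments (section 7.1), 2 time points per treatment (Appendix F).

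- Sessions: 10 × 3 = 30.
- Post-treatment scores: 30 × 2 = 60.
- Pre-treatment scores on this scale: 0.
- With one pre-treatment score per session: 60 + 30 = 90.

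At the upper limit of 300 subjects in sections 2 and 5.1, the plan gives 300 × 3 × 2 = 1,800 post-treatment scores, still with none before treatment.

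**2. Can another record stand in for the missing score?**

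- *Screening examination (7.3.1).* The target area is examined for eligibility and is not scored on this scale. Treatment may follow up to a week later, so the examination need not show the tissue as it was just before treatment 1.
- *Photographs (7.2.2, Table 1).* These are taken at baseline and immediately before treatments 2 and 3. They are graded only for improvement on the GAI scale, and the grading form (Appendix C) lists only mons pubis and labia. The plan does not say whether they come before or after the specimen.
- *Subject questionnaire (Appendix G).* It asks when redness, swelling, crusting and blistering resolved after a session. It says nothing of the state before the session.
- *Adverse event records (section 9).* These capture events. They do not grade the tissue before each treatment.

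None gives a pre-treatment value on the five-level scale.

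**3. Can the score be taken apart afterwards?** No. Appendix F has one number per time point, not split by sign or area, and step 8 of section 7.5 places the examination after both applicators have been used. A bruise at a biopsy site and diffuse redness from treatment go into the same number.

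**4. Illustration.** The documents give no frequency of prior redness. Assume that each subject independently has probability *p* of arriving at a given session with some. The expected number among 10 is 10*p*, and the chance of at least one is 1 − (1 − *p*)^10:

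| Assumed *p* | Expected of 10 | Chance of at least one |
|---|---|---|
| 5% | 0.5 | 40% |
| 10% | 1 | 65% |
| 20% | 2 | 89% |
| 30% | 3 | 97% |

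This shows how readily some ambiguity could arise in a group of 10. It does not estimate how many scores would be wrong, which also depends on how the investigator allows for what was there before.

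**The case against.** The strongest reply is that Appendix F asks for the tissue's response to treatment. The rater is told to attribute, has examined the area at screening, and has photographs taken before treatment. A reader might infer that prior redness counts as device response by rule. The documents do not support that, and the reply stands to that extent. It does not make the attribution checkable, because no starting value is written down.

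Other stronger readings also fail:

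- *Carry-over from the previous session.* Sessions are four weeks apart. Section 7.6.1 expects redness and swelling to last at most a few hours as a rule, and Appendix G asks when they resolved. Carry-over is not a credible main source.
- *Shaving as an expected irritant.* Section 7.4.1 prescribes foam or gel as a precaution, and only before the first treatment. Shaving is a possible source of redness, no more.
- *Conflict with the design label.* Section 2 says "This is a single center, baseline-controlled, prospective study", but the comparison that the plan defines against baseline is the photographic GAI at FU3. A reaction score without a baseline does not contradict the label.
- *No mild level.* The scale goes from trace to moderate, but it is ordered and has a low step. The Mild grade in section 9.1.1 belongs to a separate adverse event scale. The "mild to moderate edema lasting more than 6 hours" in section 9.3.1 concerns reactions well beyond the 30-minute window. Relabelling to make room for a mild level by merging the top two levels would lose resolution at the severe end of a safety scale.

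It is also fair to say that this is a feasibility study, that the interim review is qualitative, and that adverse events are listed separately. These facts limit the consequence but do not supply the missing value.

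**Conclusion.** The point holds in a limited form. None of the 60 scores planned for 10 subjects has a pre-treatment counterpart on this scale. Device response therefore cannot be separated, in the recorded data, from redness, swelling or bruising already present. Shaving before treatment 1 and the specimens from treated sites are plausible sources that the plan itself creates.

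The size and direction of any distortion are unknown. The conclusion rests on two assumptions: that shaving or a biopsy sometimes leaves visible marks in the scored area, and that an investigator's unrecorded allowance for them may vary. Not every specimen need matter, since section 6.2.3 lets it come from any treated site.

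This is an inexpensive improvement to a safety endpoint that has no control arm. It does not show that the planned safety data are invalid.

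**What to change.** In section 7.2.1, Table 1, the flow chart and Appendix F, add one score on the existing five-level scale. The same investigator should record it immediately before each treatment and after any specimen taken at that visit.

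In section 8.3, state that the descriptive summary and the interim safety report will show the number of subjects with a new or worsened response from that score, at each session and time point, beside the raw post-treatment score. Counts by level suit an ordinal scale better than mean differences.

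As a minor clarification, brief written definitions of the five existing levels could be added to Appendix F, with the levels themselves unchanged.

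The cost is about one minute and one entry per treatment visit: 30 extra entries, or roughly 30 × 1 = 30 minutes in all for 10 subjects. It needs no extra staff and no further invasive procedure. One limit remains: a biopsy reaction that develops during the following half hour would still appear as worsening. The pre-treatment score reduces the ambiguity without removing it.

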#### 7.2.2 Skin improvement assessment

The assessment of general improvement in skin appearance will be accomplished by an independent evaluation of photographs.

At baseline and in FU3, a photograph of each of the treated areas will be taken per the photography guidelines. A copy of the images will be sent to independent reviewers. The reviewers will evaluate, for each time point, the improvement in skin appearance in comparison to base line based on the GAI scale (See Appendix B). The results of the evaluation will be recorded in the Photographs assessment log (see appendix

Confidential 10

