#### 4 Outcome Measures

## 4.1 Primary Effectiveness Endpoints

• General skin appearance improvement at FU3 compared to baseline as assessed by independent evaluators by photographic assessment, utilizing the GAI Scale.

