#### 8.3 Study Analysis

• An intermediate safety report based on qualitative analysis of immediate and short term reaction and on AEs will be produced based on analysis of data collected immediately post treatment number one of all the enrolled subjects. This data will be used to adjust further treatments parameter. The interim

Confidential 14

- reports will not affect the continuation of the study. The study will, regardless of the interim report results, be finalized according to this protocol.
- After FU3, the photographs will be sent to independent evaluators that will grade on a GAI scale the change in skin laxity according to photograph of FU3 compare to baseline. Descriptive statistics and correlations between variables will be performed on these results.
- After FU3 the subject assessment on the change in skin laxity on a GAI scale will be analyzed. These results will be correlated with the evaluation done by the independent evaluators in order to learn on the relationships between objective and subjective improvements assessments.
- After FU3 all data collected by response and discomfort/pain level (VAS) and the 5-level short term response scale results will be analyzed using descriptive statistics.
- After FU3, the vaginal pH values will be sent to the PI for formal data entry and analysis. These results will be correlated with the evaluation done by the independent evaluators in order to learn on the relationships between objective and subjective improvements assessments.
- After FU3, the histology slides and molecular assay results will be sent to the PI for formal data entry
  and analysis and archive storage (histology slides). These results will be correlated with the evaluation
  done by the independent evaluators in order to learn on the relationships between objective and
  subjective improvements assessments.

The study reports will provide information for use in research & development, and future planned studies. Descriptive statistics and correlations between variables will be performed.

Safety: Adverse events reported will be listed, documenting course, outcome, severity, and possible relationship to the treatment.

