## 12.2 Appendix B - GAI Scale

Table 1 - Global Aesthetic Improvement (GAI) scale to be used for both investigator and subject evaluation:

(3)	Very Much Improved
(2)	Much Improved
(1)	Improved
(0)	No Change
(-1)	Worse
(-2)	Much Worse
(-3)	Very Much Worse

Confidential 22

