## 12.3 Appendix C - Photographs Assessment Log

## Independent Evaluators' Form

Subject	ID	Treated Area	Slide Set #	GAI score
(initials)				
		☐Mons Pubis ☐Labia	$\square$ Baseline + $\square$ FU1/ $\square$ FU2/ $\square$ FU3	
		☐Mons Pubis ☐Labia	$\square$ Baseline + $\square$ FU1/ $\square$ FU2/ $\square$ FU3	
		☐Mons Pubis ☐Labia	$\square$ Baseline + $\square$ FU1/ $\square$ FU2/ $\square$ FU3	
		☐Mons Pubis ☐Labia	$\square$ Baseline + $\square$ FU1/ $\square$ FU2/ $\square$ FU3	
		☐Mons Pubis ☐Labia	☐Baseline + ☐FU1/☐ FU2/ ☐FU3	
		☐Mons Pubis ☐Labia	☐Baseline + ☐FU1/☐ FU2/ ☐FU3	
		☐Mons Pubis ☐Labia	☐Baseline + ☐FU1/☐ FU2/ ☐FU3	
		☐Mons Pubis ☐Labia	$\square$ Baseline + $\square$ FU1/ $\square$ FU2/ $\square$ FU3	
		☐ Mons Pubis ☐ Labia	$\square$ Baseline + $\square$ FU1/ $\square$ FU2/ $\square$ FU3	
		☐ Mons Pubis ☐ Labia	$\square$ Baseline + $\square$ FU1/ $\square$ FU2/ $\square$ FU3	
		☐Mons Pubis ☐Labia	$\square$ Baseline + $\square$ FU1/ $\square$ FU2/ $\square$ FU3	
		☐Mons Pubis ☐Labia	$\square$ Baseline + $\square$ FU1/ $\square$ FU2/ $\square$ FU3	
		☐Mons Pubis ☐Labia	$\square$ Baseline + $\square$ FU1/ $\square$ FU2/ $\square$ FU3	
		☐Mons Pubis ☐Labia	$\square$ Baseline + $\square$ FU1/ $\square$ FU2/ $\square$ FU3	
		☐Mons Pubis ☐Labia	$\square$ Baseline + $\square$ FU1/ $\square$ FU2/ $\square$ FU3	
		☐Mons Pubis ☐Labia	$\square$ Baseline + $\square$ FU1/ $\square$ FU2/ $\square$ FU3	
		☐Mons Pubis ☐Labia	$\square$ Baseline + $\square$ FU1/ $\square$ FU2/ $\square$ FU3	
		☐Mons Pubis ☐Labia	☐Baseline + ☐FU1/☐ FU2/ ☐FU3	
		☐Mons Pubis ☐Labia	$\square$ Baseline + $\square$ FU1/ $\square$ FU2/ $\square$ FU3	
		☐Mons Pubis ☐Labia	☐Baseline + ☐FU1/☐ FU2/ ☐FU3	

Confidential 23

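### The only primary effectiveness endpoint is a photograph rating against a known baseline, and the plan has no step that hides image order from the evaluators

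*Combined protocol and SAP*

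**What the plan says.** Section 4.1 lists one primary effectiveness endpoint: "General skin appearance improvement at FU3 compared to baseline as assessed by independent evaluators by photographic assessment", scored on the GAI scale. Section 7.2.2 gives the rating procedure: "The reviewers will evaluate, for each time point, the improvement in skin appearance in comparison to base line based on the GAI scale". Section 8.3 sets the timing, "After FU3, the photographs will be sent to independent evaluators", and has them grade FU3 against baseline. Table 1 likewise places the independent reviewers' score at the end of the study.

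Appendix B gives the scale: seven categories from -3 to +3, with positive scores for improvement and negative scores for worsening. Its caption describes it as "to be used for both investigator and subject evaluation"; section 7.2.2 and Table 1 also apply it to the independent reviewers.

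The evaluators' log in Appendix C has, for each score, boxes for the treated area (mons pubis or labia) and for the slide set: baseline plus FU1, FU2 or FU3.

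On design, section 2 states: "This is a single center, baseline-controlled, prospective study". On de-identification, section 6.2.1 deletes identifying detail from images and adds: "Only the code for the Case Number in the study will appear on the records being transferred to the sponsor". Section 7.4.2.1 standardises lighting, distance, angle and position; its example file name contains the visit label Tx1.

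**The concern.** An evaluator who knows which photograph was taken after treatment may expect to see improvement and may resolve doubtful pairs in that direction. Where a concurrent control is rated the same way, part of that tendency cancels in the comparison. Here there is no such group, so any tendency passes straight into the reported GAI result.

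The analysis is descriptive, but the stakes are not trivial. Section 3.1 sets out to verify efficacy, section 8.1 states that treatment will bring improvement, and section 8.3 says the reports will inform future studies. A descriptive estimate can be biased just as a tested one can.

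**Working it through.** The plan gives no figure for rater bias and no test, success threshold or power calculation for this endpoint. There is therefore nothing to reproduce, and the check is a reading of every provision that governs the rating.

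**What the evaluator knows under the plan as written**

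- Sections 7.2.2 and 8.3: the task is to score change from baseline, so baseline is identified as the reference.
- Appendix B: the score is signed. An evaluator can assign + or - only by knowing which image is later, unless the sign is added afterwards. No such decoding step appears.
- Section 7.4.2.1: the example file name carries the visit. No recoding before review is described.
- Appendix C: the form names the visits that make up a pair. It does not say which image is which, or who ticks the boxes.

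**What the safeguards cover**

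- Independence (sections 4.1, 7.2, 7.2.2, 8.3) concerns who rates, not what the rater knows.
- De-identification (section 6.2.1) removes subject identity and describes records sent to the sponsor. It does not mention visit order or the evaluators' copies.
- Standardised photography (sections 6.2.1 and 7.4.2.1) reduces technical differences between images but leaves the order known.
- The symmetric scale allows a negative score but does not hide the direction of time.

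**What random order would change**

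Take a pair with no real change and no visible cue to order, in which the evaluator nevertheless prefers one side by g grades. With random left/right placement, the preferred image is the later one with probability 1/2. The expected decoded score is (1/2)(+g) + (1/2)(-g) = 0. With known order there is no such guarantee: if expectation favours the later image, the expected score is above 0 by an amount the documents cannot supply.

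**Can the present scale be kept?**

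Later image better at 3 grades, earlier image better at 3 grades, and no change: 3 + 3 + 1 = 7 outcomes, against 7 categories in Appendix B. The numerical range is preserved; the verbal anchors must be preserved as well.

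**Workload**

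Inputs: 10 subjects (section 8.2) and 2 areas (Appendix C).

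- Baseline/FU3 pairs: 10 × 2 = 20.
- If FU1 and FU2 pairs are also rated: 20 × 3 = 60.
- At the 300-subject ceiling in section 2: 300 × 2 = 600, or 600 × 3 = 1,800. Appendix I makes that expansion subject to further IRB review.

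**The case against.** The strongest case on the other side is that this is a feasibility study of 10 subjects, with descriptive statistics and no success rule. It already uses independent evaluators, a symmetric scale and controlled photography. GAI is by nature a before-and-after scale, and no bias has been quantified. This stands as a limit on how much weight the point can carry. It does not supply the missing masking, and the plan's aim is to verify efficacy.

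A reader might also infer four stronger things, which the documents do not support.

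- *That the Appendix C form itself discloses image order.* It labels the pair, not each image; a masked pair could be recorded on the same form. Order is known through the rating instruction and the signed scale. The example file name would add to this if the names reach the evaluators unchanged.
- *That the three planned correlations (with subject GAI, vaginal pH and histology/molecular results) are biased too.* A uniform shift c leaves a correlation unchanged: corr(X + c, Y) = corr(X, Y), and ranks are unchanged as well. Distortion would need clipping at the top of the scale, or bias that varies with the other measure. Nothing in the plan shows either.
- *That section 8.3 presumes an expectation-free score.* It says results will be "correlated with the evaluation done by the independent evaluators in order to learn on the relationships between objective and subjective improvements assessments". That may simply contrast third-party ratings with self-report, and the same sentence is used for pH and histology.
- *That hair or biopsy marks reveal the order.* Section 7.4.1 mentions shaving only before the first treatment, and biopsies precede FU3. But section 6.2.3 allows biopsy at any treated site, including sites Appendix C does not rate, and no passage says a mark would be visible. This is conjecture and not part of the defect.

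**Conclusion.** The point holds as an omission in the method for the only primary effectiveness endpoint. Followed as written, the plan yields a subjective rating made with image order known, in a study with no concurrent control. The GAI result is therefore open to expectation bias.

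The size and presence of that bias cannot be established from the documents. No error rate is claimed either, because computing one would require a success rule that the plan does not contain. The conclusion rests on the text of the rating procedure and on the ordinary premise that a rater's expectation can influence a subjective score. It does not extend to the safety endpoints in section 4.3 or to the planned correlations.

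The change should be made: the gap is clear, its effect is unknown, and the remedy is inexpensive.

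**What to change.** Amend sections 7.2.2 and 8.3 and Appendix C as follows.

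1. Give evaluators copies of each baseline/FU3 pair, and of any FU1 or FU2 pair that is rated, under a random code and in random left/right order. Remove visit labels from the file names supplied and from the evaluators' form.
2. Have the evaluator state which image looks better, or no change, and grade the difference in the Appendix B terms (improved, much improved, very much improved).
3. Let existing study personnel hold the link between the random code and the section 7.3.2 subject identifier. The original photographs, which are source documents under section 10.5, stay unchanged.
4. After scores are locked, convert to the signed Appendix B score: later image better = +1 to +3, earlier image better = -1 to -3, no change = 0.

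Optionally, note visible differences such as hair state at each photograph. This is secondary.

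The cost is a coding list, a revised form and a score-lock step, with no extra reader or visit. Grading already takes place after FU3, so coding can be fitted in before images are sent. Because photographs are retained under section 10.10, a masked read would still be possible later, though none is planned.

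The downsides are a possibly less favourable estimate, imperfect masking if visible cues such as hair regrowth remain, and a rating task slightly different from the subject's own GAI. There would still be no concurrent control.
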